Why focus on the LPG via tDCS to understand the contribution of this shared neural circuit to NPS? Our previous work on NPS-shared neural circuit shows that while different NPS are associated with the same 10 frontal-temporal-striatal regions, the strength of functional connectivity (FC), as well as its directionality, varies for different NPS. For example, the strength of most FCs in MCI/AD patients with a depressive symptom is lower than that in patients without this symptom, while the strength of most FCs are higher in patients with an anxiety symptom. Across NPS, however, LPG is the only region that has lower FCs with frontal and striatal regions within the circuit whenever a NPS is present.³ LPG, parallel to C3 in the 10/20 EEG system,⁵ is one of the most frequently examined and effective tDCS targets modifying affective, psychiatric, and psychosomatic symptoms, in addition to motor function.⁶⁻⁸ Administering anodal tDCS also enhances the strength of FCs linking LPG to frontal and limbic regions that are part of the NPS-shared neural circuit.⁹⁻¹² Notably, our feasibility study demonstrated our readiness and safety of administering anodal tDCS to C3 in older adults. Synthesizing these separate lines of evidence, we **hypothesize** that administering anodal tDCS to C3 in patients with NPS will result in enhanced activation of LPG and reorganization of NPS-shared neural circuit, both of which will improve NPS.

Aim 1. Determine the effect of tDCS on NPS-shared neural circuit. **H:** After intervention, the active group, relative to the sham group, will have a greater increase in LPG activity, indexed by greater activation in LPG in response to a visual attention task (H1a) and greater increase in resting FC strength between LPG and other regions within the NPS-shared neural circuit (H1b).

Aim 2. Determine the relationship between NPS-shared neural circuit and study partner-report NPS. **H:** After intervention, the active group, relative to the sham group, will have greater improvement in study partner-rated NPS in terms of lower severity and fewer co-existing symptoms (H2a). Changes in LPG task-induced activity combined with an LPG-seeded NPS-shared neural circuit will contribute to the

improvement in study partner-rated NPS across groups (H2b).

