disturbing for cognitive and functional decline¹; (2) a neural circuit (i.e., NPS-shared neural circuit) supports multiple NPS and links to study partner-rated NPS and AD pathophysiology³; (3) the strength of FCs within the NPS-shared neural circuit varies across individual NPS, with LPG exhibiting greater FC strengths with frontal and striatal regions within the circuit but weaker FC strengths with other regions, the latter of which is linked to higher chances of presenting NPS³; (4) LPG is a hub region that regulates visual attention and processing speed^{4,43,44}; (5) anodal tDCS targeting LPG enhances brain synchronization and whole-brain resting-state functional connectivity between LPG and its neighboring regions (particularly frontoparietal regions) or between LPG and caudate⁹⁻¹²; (6) anodal tDCS targeting LPG also modifies affective, psychiatric, and psychosomatic symptoms (e.g., humor, appreciation, anxiety, pain)⁶⁻⁸.

We hypothesize that anodal tDCS stimulating LPG can affect LPG activation (indexed by enhanced neural efficiency during the visual attention task) and its connectivity with other regions within the NPS-shared neural circuit, which, in turn, will reorganize the NPS-shared neural circuit and improve study partner-rated NPS (**Figure 2**). Validating these hypotheses will extend separate bodies of literature on the symptomatic understanding of multiple NPS, neural mechanisms underlying NPS, and the impact of tDCS on neural and behavioral effects, as well as facilitate an explicit elaboration of a shared neural mechanism underlying multiple NPS in MCI. This elaboration has strong potential to inform treatment development for managing multiple NPS simultaneously by addressing the shared neural circuit as the primary therapeutic target. This proposal's significance is further underscored by the implications of our model for potentially preventing AD pathology: our pilot work suggests the NPS-shared neural circuit predicts the trajectory of AD pathology progression, indexed by a change in cerebrospinal fluid A β /ptau ratio. If the neural circuit is modifiable via tDCS applied to the key region within the circuit, this approach may be applicable to

delaying AD pathology from developing and benefit other clinical domains, such as cognitive

deficits and impaired functional **Figure 2. Conceptual framework**

independence, thereby potentially slowing overall AD progression.

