4. STUDY DESIGN

This is a Stage 0 study for mechanistic understanding. We will recruit older adults with study partner-rated NPS that has worsened in the past 2 years. Our previous study shows that this will capture

the most detrimental type of NPS.¹ We will focus on the MCI group, since understanding and modifying NPS among this group may assist in slowing the progression of dementia. See Table 1 for the overview of assessment and intervention timeline.

- Double-blind randomized controlled trial of 40 participants and their study partner subjects; all eligible and interested intervention subjects will be enrolled and undergo a baseline assessment, MRI scan, and blood draw; PI, staff conducting follow-up assessments and intervention subjects and their study partner subjects will be blinded. Interventionists and data managers will know randomization.
- After baseline, all intervention subjects will be randomly assigned to one of two groups - active anodal or sham C3 tDCS. A MATLAB block-based randomization code will be used to randomly assign study ID to group. Each study ID-group pairing will be printed and placed inside a sealed envelope labeled with only the study ID to ensure blinding. After an intervention subject and their partner subject finish baseline assessments, the interventionist or data manager will open the randomization envelope to assign the respective study ID.
- All intervention subjects will undergo a total of fourteen (14) 20-minute tDCS sessions over the course of four weeks: ideally, five times a week for two weeks, followed by twice a week for an additional two weeks. However, we will extend the intervention for additional two weeks for make-up sessions.
- Assessments will occur at baseline, within 2-week after finishing intervention (post-intervention assessment), and 4 to 6 weeks after post-intervention assessment (follow-up assessment).
- Unblinding will occur upon the completion of the follow-up assessment. We will not provide those in the sham group with the active tDCS procedure.

Primary endpoints:

- Resting-state and visual attention task-related fMRI;⁴⁵

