17. DATA ANALYSIS PLAN

This is a pilot study for mechanistic understanding of the relationship between our previously discovered NPS-shared neural circuit and study partner-rated NPS. Results from the study will provide information for accurately calculating effect size for future clinical trial. Regardless, in addition to follow the rule of 12-20 subjects per group for a pilot clinical trial, we will calculate the sample size. The sample size calculation is based on the effect size of LPG related tDCS on visual attention performance ($f = 0.45$, $n = 36$). Additionally, the effect size of correlation between NPS-shared neural circuit and patient-report NPI-Q was $r^2 = 0.70$ in our previous study³ – here we use a much more conservative estimation at $r^2 = 0.20$, the sample size will be $n = 37$. All of these calculations are based on power at 0.80 and alpha at 0.05. For an 8-week follow up, we estimate 10% attrition rate. Therefore, we propose a total of 40 intervention subjects for the study.

Aim 1. Determine the effect of tDCS on NPS-shared neural circuit. H: After intervention, the active, relative to sham group will have greater increase in LPG activity, indexed by greater activation in LPG in response to visual attention task (H1a) and greater increase in resting FC strength between LPG and other regions within the NPS-shared neural circuit (H1b). To assess the activation pattern in LPG, we will conduct GLM analysis with the SPM software. The coefficients of GLM corresponding to LPG will be analyzed through hypothesis testing. We will first conduct a simple t-test to evaluate whether the intervention increases LPG activation for each group (at 4 or 8 weeks), and then a more powerful two sample kernel test will be used to test activations distribution difference between groups.⁵¹ Similarly, we will take the FCs between LPG and other regions as a multivariate covariate and apply the two-sample kernel test to evaluate group difference in the change of LPG FC pattern after intervention (at 4 or 8 weeks). In addition, simple multiple testing for each connection will be used as a screening procedure to identify a subset of connections included in the kernel test.

Aim 2. Determine the relationship between NPS-shared neural circuit and study partner-report NPS.

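### H1a predicts a larger LPG rise on active than on sham tDCS, but section 17 plans no signed between-arm estimate with a confidence interval for it

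*Combined protocol and SAP*

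**What the plan says.** Section 1 (Aim 1) states the hypothesis as a signed comparison: "the active group, relative to the sham group, will have a greater increase in LPG activity". For H1a the measure is LPG activation on the visual attention task. Section 4 lists "Resting-state and visual attention task-related fMRI" under primary endpoints.

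Section 17 (Aim 1) gives the analysis of H1a in three steps:

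- A general statement: "The coefficients of GLM corresponding to LPG will be analyzed through hypothesis testing".
- A test within each arm: "We will first conduct a simple t-test to evaluate whether the intervention increases LPG activation for each group (at 4 or 8 weeks").
- A comparison of arms: "a more powerful two sample kernel test will be used to test activations distribution difference between groups".

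For H1b the plan will "apply the two-sample kernel test to evaluate group difference in the change of LPG FC pattern after intervention". The H1a sentence does not say whether its kernel test uses change or post-intervention level, or whether its input is the LPG mean or the voxels.

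The only model with a visit-by-group term is the mixed model for H2a, later in section 17, and it covers NPI measures.

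**The concern.** A signed, comparative hypothesis needs a signed comparison of arms. A t-test in each arm asks whether that arm changed, not whether it changed more than the other. A two-sample kernel test asks whether two distributions differ in any respect. Rejection can come from a higher active mean, a lower active mean, or a difference in spread alone. Neither step produces an active-minus-sham difference with its uncertainty, so a primary endpoint would be reported as p-values without the estimate that H1a is about.

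Section 2 adds to the need for a stated rule, because it words the expectation without a sign: stimulation "can affect LPG activation (indexed by enhanced neural efficiency during the visual attention task"). Greater efficiency need not mean greater activation, so section 17 should say which result supports H1a.

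**Working it through.** **1. What each planned step can show**

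| Step | Compares arms | Has a sign | Gives an estimate with CI |
|---|---|---|---|
| t-test in each arm | no | yes, within the arm | not stated |
| two-sample kernel test | yes | no | no |
| H2a mixed model | yes | yes (average change by group) | NPI only; no CI stated |

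No other sentence in section 17 fills the empty place for H1a. This conclusion needs no numerical assumption.

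**2. Inputs for an illustration**

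Section 17 gives f = 0.45 for visual attention performance, n = 36, 10% attrition, a total of 40, and alpha 0.05. With two equal groups d = 2f = 0.90. The total reproduces as 36 / 0.9 = 40, and 40 × 0.9 = 36 leaves 18 per arm (1:1 allocation assumed). The 36 itself does not follow from a plain two-group t-test at 80% power: 20.4, so 21 per arm (42 in all) two-sided, or 16 per arm (32) one-sided. The test family is not stated, so this does not show an error, and the present point does not depend on it.

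The documents give no LPG effect, baseline-post correlation, kernel or bandwidth. Assumed: one normal LPG value per participant, change SD 1, a gap of 0.9 SD borrowed from the performance figure, two-sided 0.05, baseline SD 1, and slope of post on baseline 0.5.

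**3. A signed contrast with 18 per arm**

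- *t-test on change.* Noncentrality = 0.9 × √(18/2) = 2.70 on 34 df; power 0.75. The 95% CI half-width is 2.032 × √(2/18) = 0.68 SD.
- *ANCOVA.* Change = −0.5 × baseline + residual, so 1 = 0.25 + σ² and σ = 0.866. Noncentrality = (0.9 / 0.866) × 3 = 3.12 on 33 df; power 0.86, and 0.83-0.86 in simulation, where chance baseline imbalance costs a little. Half-width is 2.035 × 0.866 × √(2/18) = 0.59 SD.

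**4. The kernel test on the same scalar input**

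Simulated as a permutation test with a Gaussian kernel at the median bandwidth (two usual scalings, 299 permutations, 2,000-3,000 runs per setting):

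- Active 0.9 SD above sham: rejects in about 0.56-0.64 of trials.
- Active 0.9 SD below sham: rejects about as often (0.56 in each direction in a matched pair of runs).
- Equal means, one arm with twice the SD: rejects in about 0.43, against about 0.06 for a Welch t-test.

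**5. The two steps read in sequence**

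Equal true change of 0.5 in both arms, in units of the active-arm SD. The pattern that would look like support is *active rises significantly, sham does not, kernel test rejects*.

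| Sham SD / active SD | Pattern occurs | ANCOVA interval above zero |
|---|---|---|
| 1 | 0.02 | 0.02 |
| 1.25 | about 0.04 | 0.02 |
| 1.5 | 0.09 | 0.02 |
| 2 | 0.21 | 0.03 |

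The ratios are illustrations, not document figures. If the active arm has the doubled SD, the mirror pattern (sham rises, active does not, kernel test rejects) occurs in 0.22-0.23.

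**6. Voxel input**

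Suppose 20% of 50 voxels shift by 0.9 SD, with between-voxel correlation 0.5 (assumed). The regional mean then shifts by 0.2 × 0.9 = 0.18, with SD √(0.5 + 0.5/50) = 0.714, so d = 0.25 and a t-test on the LPG mean has power 0.11. The kernel test on the voxels has 0.63-0.76. Here the plan's claim of greater power is right.

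**The case against.** **The arm means show the direction.** This stands. A reader might infer that a kernel rejection leaves the direction unknown. In every simulated trial with equal spread, a 0.9 SD gap and a kernel rejection, the difference in arm means had the right sign. With equal spread and equal change the sequence points to active in only about 2% of trials. What remains missing is a planned signed test and an interval.

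**The input may be voxels.** This also stands. Section 17 speaks of an activation pattern, and H2b uses voxel-level change. The scalar figures apply only if the kernel test receives one LPG value per participant. For a focal pattern the kernel test is the better detector, which is why it should be kept. It still gives no sign and no estimate.

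**The unequal-spread result depends on assumed ratios.** True; at 1.25 it is small. Nor does the plan name the three-part pattern as a success criterion. It is how a reader would be inclined to take such a result.

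**This is a Stage 0 pilot.** That lowers the stakes. A reader might infer from "Results from the study will provide information for accurately calculating effect size for future clinical trial" that the missing interval undermines the sizing of the next trial. The documents do not support this: the sentence does not name LPG activation, and section 1 describes the future study as a Stage 2 trial addressing NPS, whose effect is modelled under H2a.

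**The H2a model is no gold standard.** Fair: it states no CI, and its composite test is undirected too. It does show that the plan can model a between-arm comparison over visits.

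**Conclusion.** The point holds and should be fixed. As written, section 17 cannot deliver the quantity that H1a is about: an active-minus-sham difference in LPG activation with its uncertainty. That follows from the text alone.

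The numbers rest on assumptions (18 per arm, normal scalar LPG value, 0.9 SD gap, slope 0.5). Under them the kernel test has power of about 0.56-0.64, against 0.75 for a t-test and about 0.85 for ANCOVA, so the claim of greater power does not hold for scalar input. Unequal spread with equal true change gives an apparent H1a result in about 9% and 21% of trials at ratios of 1.5 and 2, against 2-3% for the ANCOVA interval. The plan is not shown to be misleading in general: with similar spread it rarely points the wrong way.

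**What to change.** In section 17, Aim 1:

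- Add for H1a an ANCOVA of the mean LPG task coefficient at the post-intervention visit on group and its baseline value. Report the active-minus-sham difference with its 95% CI. Make the follow-up visit secondary.
- Base any statement that mean LPG activation rose more in active than in sham on that contrast.
- Keep the kernel test, on change from baseline, as the test of a difference in pattern or distribution. Report it as that, not as evidence of a greater increase.
- Label the within-arm t-tests descriptive.
- Limit the claim of greater power to multivariate voxel input.

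Cost: SAP wording only. The baseline, post-intervention and follow-up scans are already in Table 1, and no sample-size figure changes. The downside is that an effect confined to a few voxels may not move the regional mean (power 0.11 for a t-test on the mean in the example above; baseline adjustment would recover only a little). That is the reason to keep the kernel test beside the ANCOVA.

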8. STUDY PROCEDURES

COVID-19 Safety Regulations:

To ensure appropriate safety precautions when conducting in-person study procedures, the process for conducting in-person visits outlined in the Guidance for Human Subject Research webpage (<https://www.urmc.rochester.edu/coronavirus/coronavirus-research/guidance-for-researchers/human-subjects-research.aspx>) will be followed. We will remain vigilant about any further changes to the research reboot guidance.

This study will screen participants and their study partner subjects in two steps (phone-screening and secondary interview, including capacity to consent and informed consent). Eligible participants and their study partner subjects will be enrolled, and participants will be asked to complete a baseline cognitive assessment, MRI scan, and blood draw. The participant will then be randomized and start their intervention program within two weeks. Each program will consist of 14 tDCS sessions over 4 weeks. Follow-up cognitive assessments and MRI scans will occur at 4- and 8- weeks after baseline.

Screening: Potential participants who respond to our recruitment strategies and initiate contact with us will be carefully screened for eligibility and safety through a 2-step screening process:

(1) Phone screening (approximately 20 minutes for intervention subject and partner subject)

respectively): Upon over-the-phone contact, staff conducting the screening will explain the study using the phone screening script, answer any questions. If the participant is interested, the staff member will obtain their verbal consent to be administered the phone screening questions by signing and dating the verbal consent for screening form. Staff will collect basic self-reported health history to check for obvious contraindications for MRI or tDCS and to ensure a homogenous sample. Responses to these basic health history related items may need to be confirmed by their physician to ensure safety of MRI procedure are met. Identification of a “study partner subject” willing to participate in the study with the participant. Administration of the Neuropsychiatric Inventory Questionnaire (NPI-Q, a short form version of the NPI) with the study partner subject (after obtaining verbal consent from the study partner subject to be asked these questions) will also be conducted as part of this brief initial screening step,

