H2a. After intervention, the active, relative to sham group will have greater improvement in study partner-rated NPS in terms of lower severity and fewer co-existing symptoms: We will fit linear mixed-effect models for changes in NPS: $Y_i = X_i\beta + Z_iu_i + \epsilon_i$, where $Y_i = (y_{i1}, \dots, y_{iT})$ represents the NPI measures across time, X_i is a $T \times p$ design matrix for the fixed effects and Z_i is a $T \times q$ matrix for the random effects. The models will include fixed effects such as data collection visit (categorical variable), group, visit and group interaction, and covariates identified as being imbalanced among groups. Stepwise variable selection based on Akaike Information Criteria will be used to select the fixed effects for inclusion. A random participant-specific effect will be included to account for correlation between visits for the same participant. The model-based average within-group change will be computed for each outcome at 4 and 8 weeks. This will allow us to rank the groups in terms of average within-person gains in each outcome. We will conduct a composite hypothesis test to assess if the changes at 4 or 8 weeks differ by groups (similar to a one-factor ANOVA but accounting for repeated measures). **H2b. FC change in NPS-shared neural circuit will contribute to the improvement in study partner-rated NPS across groups:** We will perform epsilon-intensive support vector regression (SVR) with RBF kernel using LIBSVM library.⁵² The Leave-One-Out-Cross-Validation scheme will be applied: each intervention subject will be designated as

the test sample once, while the remaining intervention subjects will be used as training sample. All training sample's features (change of voxel activation from the task or change of FCs from the NPS-shared neural circuit after intervention) will be trained to predict the test sample's outcome (change of NPI severity or frequency score). We will then perform model fitting of the raw and predicted NPI using linear function ($f(x)=ax+b$). Adjusted R^2 will be used to estimate goodness of fit for the model.

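### The H1a between-arm test does not say whether or how baseline LPG activation enters; it should specify a baseline-adjusted comparison and name the visit

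*Combined protocol and SAP*

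**What the plan says.** Section 4 lists resting-state and visual attention task fMRI as the primary endpoints and says that "all eligible and interested intervention subjects will be enrolled and undergo a baseline assessment, MRI scan, and blood draw"; randomisation follows. Section 8 repeats this ("participants will be asked to complete a baseline cognitive assessment, MRI scan, and blood draw"), and Table 1 schedules further scans at both post-intervention visits.

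In Section 1 the Aim 1 hypothesis is that "the active group, relative to the sham group, will have a greater increase in LPG activity", with H1a indexed by task activation in LPG and H1b by resting connectivity. Section 17 handles Aim 1 in three steps:

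- H1a within arms: "We will first conduct a simple t-test to evaluate whether the intervention increases LPG activation for each group (at 4 or 8 weeks".
- H1a between arms: "a more powerful two sample kernel test will be used to test activations distribution difference between groups".
- H1b between arms, introduced by *Similarly*: "apply the two-sample kernel test to evaluate group difference in the change of LPG FC pattern after intervention".

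For H2b, also in Section 17, the activation feature is the "change of voxel activation from the task".

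**The concern.** The hypothesis is comparative and about increase: "the active, relative to sham group will have greater increase in LPG activity". The per-arm t-tests look at increase but do not compare the arms. The kernel test compares the arms but does not say what it is fed: post-intervention activation, change from baseline, or a baseline-adjusted value. It also does not say which visit. The same section writes *change* for H1b and H2b, so the two halves of the primary endpoint may be tested on different kinds of quantity.

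With about 18 completers per arm, this choice affects power. If baseline is not used, stable differences between people in LPG activation stay in the error term, and a chance difference between arms at baseline carries into the result. If a raw change score is used, the noise of the baseline scan is added in full. Section 17 also intends the results to supply effect sizes for a later trial, so precision matters even in a Stage 0 pilot.

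**Working it through.** **Inputs from Section 17.** f = 0.45 (taken from visual attention performance, not LPG activation), n = 36, power 0.80, alpha 0.05, 10% attrition, total 40.

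**Assumptions.** 1:1 allocation; two-sided test; 36 completers, 18 per arm; d = 2f = 0.90 on the post-intervention value; one mean LPG coefficient per participant; equal SD (set to 1) at each scan; scan-to-scan correlation rho, which the documents do not give.

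**The plan's own figure.** 36/0.90 = 40 reproduces the total. The n = 36 itself does not follow from f = 0.45 in a plain two-group comparison. The two-sided requirement is 40 (normal approximation) or 42 (t), the one-sided requirement is 32, and two-sided t power at 36 is 74.6%. A repeated-measures between-group F test does give 36 with an unstated correlation (for example two measures at 0.7). The sizing therefore does not reveal which H1a quantity was meant.

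**Mean-based comparison.** With 18 per arm the noncentrality is the standardised effect times √(18/2) = 3.

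- Post only: SD 1; effect 0.90; noncentrality 2.70; 34 df.
- Change: SD √(2(1−rho)); at rho 0.5 this is 1, so the noncentrality is again 2.70.
- ANCOVA: residual SD √(1−rho²); at rho 0.5 this is 0.866, effect 0.90/0.866 = 1.039, noncentrality 3.12; 33 df.

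| rho | Post only | Change (gain) | ANCOVA (gain) |
|---|---|---|---|
| 0 | 74.6% | 45.8% (−28.8) | 74.6% (−0.1) |
| 0.3 | 74.6% | 60.1% (−14.5) | 78.4% (+3.8) |
| 0.5 | 74.6% | 74.6% (0.0) | 85.7% (+11.0) |
| 0.7 | 74.6% | 92.3% (+17.7) | 95.6% (+21.0) |
| 0.8 | 74.6% | 98.6% (+23.9) | 99.2% (+24.6) |

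Gains are in percentage points over post only, from unrounded powers. At rho 0.5 the ANCOVA gain is 8.3 points for d = 0.5 and 12.2 for d = 0.8. With all 40 evaluable and d = 0.90 it is 10.0 (79.2% to 89.3%).

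**Kernel test.** Simulated Gaussian-kernel permutation test, 18 per arm, 4,000 trials per setting. *Residual* means residuals from a regression of post on baseline, pooled over arms without an arm term. *Narrow* is the kernel exp(−D²/median) and *wide* is exp(−D²/(2·median)), where D is the distance between two participants' values and the median is that of D².

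| rho | Post → residual, narrow | Post → residual, wide | Raw change, narrow |
|---|---|---|---|
| 0.3 | 56% → 58% | 63% → 65% | 42% |
| 0.5 | 55% → 68% | 63% → 74% | 56% |
| 0.7 | 54% → 84% | 62% → 89% | 80% |

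A separate run at rho 0.5 with the narrow kernel gave 54.6% (post), 54.4% (change) and 66.5% (residual). Each simulated power near 55% has a standard error of about √(0.55 × 0.45/4000) = 0.8 points. The gains are best read as about 2–3, 10–13 and 27–30 points. With no effect, rejection rates were 4–6% for all the tests (narrow kernel, 1,500 trials).

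**Chance imbalance.** The SE of the baseline difference is √(2/18) = 0.333 SD. A gap of at least 0.3 SD (0.9 SE) occurs in 37% of such trials, and one of at least 0.5 SD (1.5 SE) in 13%. A 0.5 SD gap moves a post-only contrast by rho × 0.5, which is 0.15 to 0.35 SD for rho 0.3 to 0.7.

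**The case against.** The strongest reply is that change was meant. The hypothesis speaks of increase, the first half of the same sentence tests an increase, the next sentence opens with *Similarly* and tests change, and H2b needs activation change anyway. This stands to the extent that the plan does not exclude baseline. A reader might infer that the plan tests post-treatment activation and throws the baseline scans away, but the text does not say so. Nor does it say the opposite: H1a is indexed by greater activation where H1b is indexed by greater increase in connectivity, so the post-only reading is also open. Reading it as change does not close the point, because raw change is no better than post-only at rho 0.5 and worse below it.

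A second reply is that randomisation already makes a post-only comparison valid. That is correct. Chance baseline gaps are covered by the significance level, and the simulated error rates agree. The imbalance figures describe ordinary sampling variation that adjustment would remove.

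A third is that the power figures are fragile. This stands too. Rho is assumed, d = 0.90 is borrowed from a behavioural outcome, and Section 17 speaks of an activation pattern and of coefficients. If the kernel test is fed many voxels rather than one mean, these figures need not carry over and the adjustment takes more than one regression.

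**Conclusion.** The point holds as a gap in specification with a cost in efficiency. The one H1a comparison of the randomised arms states no link to baseline and no visit. Baseline adjustment is about as good as, or better than, both post-only and raw change at every correlation examined. The documents do not support calling the planned test biased, and they do not support a single figure for power lost. Any gain belongs to baseline adjustment specifically, not to merely using paired scans, and it depends on rho. Under the assumptions above, ANCOVA gains from about 0 points at rho 0 to 11 at 0.5 and 21 at 0.7. The kernel test gains from about 2–3 points at 0.3 to 27–30 at 0.7. If rho is near 0.3 or lower, the practical benefit is small and the main value lies in a defined test that matches the hypothesis.

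**What to change.** In Section 17, Aim 1, state that the H1a arm comparison uses baseline-adjusted LPG coefficients, and name the visit at which it is made. Choose one of two forms:

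1. Regress the post-intervention LPG coefficient on the baseline coefficient, pooled over arms and without an arm term. Apply the kernel test to the residuals, with a permutation p-value that respects the block randomisation.
2. Fit ANCOVA of the post-intervention LPG coefficient on arm and baseline coefficient.

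These are not equivalent. The first compares distributions and the second compares means, so the plan should say which one is the H1a test. If the input is voxel-wise, state how each voxel is adjusted.

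The cost is a short text change and about one degree of freedom, plus a simple prespecified rule for a missing or unusable baseline scan, such as imputing the baseline value. No new scans or participants are needed.

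### Aim 1 names no primary visit and no multiplicity rule for its two primary fMRI hypotheses; if a result at either visit counts, each carries about 7–10% false-positive risk rather than 5%

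*Combined protocol and SAP*

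**What the plan says.** - Section 4 (Study Design) gives the primary endpoints as "Resting-state and visual attention task-related fMRI". The two modalities stand together, with no order and no visit.
- Section 8 and Table 1 schedule MRI at baseline and at two later visits, post-intervention and follow-up.
- Section 17, Aim 1, H1a: a t-test will "evaluate whether the intervention increases LPG activation for each group (at 4 or 8 weeks"). A two-sample kernel test then compares the groups, and no visit is attached to it.
- Section 17, Aim 1, H1b: the plan will "apply the two-sample kernel test to evaluate group difference in the change of LPG FC pattern after intervention (at 4 or 8 weeks"). Here the two visits are attached to the between-group test itself.
- H1a and H1b are joined by the word and. There is no statement of whether one or both must succeed.
- Section 17, sample size: "All of these calculations are based on power at 0.80 and alpha at 0.05". This is the only significance level given in the plan.
- Section 17, H2a, for the secondary NPI endpoint: "We will conduct a composite hypothesis test to assess if the changes at 4 or 8 weeks differ by groups". That is one test covering both visits.

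**The concern.** With two post-baseline scans and no named primary visit, the analyst can call a hypothesis supported on whichever visit is significant. Each hypothesis then gets two chances, and its error rate exceeds 0.05. The secondary endpoint is protected by a composite test, while the primary endpoints are not.

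Two uses of the results are affected. Section 1 sets out to confirm a causal link between the circuit and symptoms, and Aim 1 is the step that shows stimulation moves the circuit. Section 17 also says the results will supply the effect size for a future trial. An estimate taken from the better of two visits is too large on average, which would make that trial too small.

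**Working it through.** **1. What the stated 0.05 refers to.** Inputs from section 17: r² = 0.20, power 0.80, alpha 0.05, n = 37. By Fisher's z, n = ((1.960 + 0.842) / atanh(√0.20))² + 3 = (2.802 / 0.481)² + 3 = 36.9, so 37. The figure reproduces with a two-sided 0.05; one-sided gives 30. The 0.05 is therefore the level of a single two-sided test. The total also follows: with the 10% attrition, 36 / 0.9 = 40. (The n = 36 for f = 0.45 does not reproduce as a plain two-group comparison, which needs 40 to 42 in total. That is a separate matter.)

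**2. One hypothesis, either visit.** If the visits were independent, the risk is 1 − 0.95² = 9.75%. They are not independent, because both changes subtract the same baseline scan. With equal variances and an equal correlation r between any two of the three scans, the correlation of the two changes is (1 − r) / (2(1 − r)) = 0.5. The documents give no value, so a range is shown.

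**3. Both hypotheses.** If either counts at either visit, independence gives 1 − 0.95⁴ = 18.5%. If both are needed, each at either visit, and both nulls hold, independence gives 0.0975² = 1.0%.

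Correlated cases come from 1,000,000 draws of four two-sided normal statistics, with correlations between visits and between hypotheses multiplied together:

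| Between-visit correlation | One hypothesis, either visit | Either hypothesis, H1a–H1b correlation 0 | Either hypothesis, H1a–H1b correlation 0.5 | Both needed, both nulls true (correlation 0 to 0.5) |
|---|---|---|---|---|
| 0 | 9.75% | 18.5% | 17.3% | 1.0–2.2% |
| 0.5 | 9.1% | 17.4% | 16.2% | 0.9–2.0% |
| 0.7 | 8.3% | 16.0% | 14.9% | 0.7–1.8% |
| 0.8 | 7.8% | 15.0% | 14.0% | 0.6–1.7% |
| 0.9 | 7.0% | 13.6% | 12.6% | 0.5–1.5% |

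If both are needed but only one null is true, the risk is at most that of the single hypothesis, about 7–9.75%.

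**4. Does this carry over to a kernel test?** A permutation kernel test was simulated with assumed inputs: 9 connections (10 regions less LPG), 20 per arm, correlation 0.3 between connections and 0.5 between visits. It rejected 4.7% of the time at one visit and 8.9% at either, in line with 9.1% above. These runs omit the connection screening that section 17 describes without a threshold. With screening at p < 0.05 on the same data, not repeated within the permutations, the rates were about 17% and 29%. The table is therefore not an upper bound for H1b.

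**5. Effect-size bias.** Assume a scalar summary of change, equal true effects at both visits and 20 per arm. The larger of two estimates exceeds the truth on average by √((1 − ρ)/π) standard errors, and one standard error is √(2/20) = 0.316 SD. At ρ = 0.5 this is 0.399 × 0.316 = 0.13 SD; at ρ = 0.7 it is 0.309 × 0.316 = 0.10 SD.

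**The case against.** The strongest reply is that the plan never says the better visit will be chosen. H2a uses the same phrase about 4 or 8 weeks for a single composite test, so in Aim 1 it may be loose shorthand for something similar. This stands as far as it goes: the inflation depends on how the phrase is applied. But Aim 1 describes no joint test, and a reader cannot tell which analysis will be run.

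A reader might also infer that there are four primary tests, that any one of them would establish Aim 1, and that the overall error is therefore about 16–19%. The documents do not support this, for four reasons:

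- H1a's mention of two visits belongs to the within-group t-tests. The test that bears on active against sham leaves its visit open.
- H1a and H1b are joined by and, and no rule makes one of them sufficient.
- The 0.05 is the sample-size level, not a declared familywise rate.
- Even on the either-hypothesis reading, 16–19% needs a between-visit correlation of no more than about 0.7 and nearly independent hypotheses. The wider range is about 13–19%.

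Finally, this is a Stage 0, proof-of-concept pilot. That lowers the consequence of a false positive. It does not remove the point, because the plan uses formal tests, a powered sample size and a stated intention to carry the effect size forward.

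**Conclusion.** The gap is real: two primary fMRI hypotheses, two post-baseline scans, no primary visit and no multiplicity rule. If success at either visit counts, the false-positive risk is about 7–10% for each hypothesis, for between-visit correlations from 0.9 to 0. For the pair, the risk is about 13–19% if either suffices, and about 0.5–2% if both are needed and both nulls hold. The plan does not choose between these readings, so none can be stated as its error rate.

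All the figures assume one between-group test per hypothesis and visit at a two-sided 0.05, with no connection screening. The upward bias of about 0.10–0.13 SD from reporting the better visit holds under the assumptions given with it. The point should be addressed but does not threaten the design.

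**What to change.** In section 17, Aim 1:

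1. For each of H1a and H1b, state that the between-group comparison is made either at one named primary visit (for example the post-intervention assessment, with the follow-up visit secondary) or as one joint test over both visits, as H2a already does. For the kernel test, stacking each participant's two changes into one vector would do this; a rule is then needed for a missing scan.
2. Identify the visit by its event. The 4- and 8-week labels in section 8 count from baseline, but the permitted windows (2 weeks to start, 4 weeks of sessions, 2 make-up weeks, 2 weeks to assessment) can put the post-intervention scan at 2 + 4 + 2 + 2 = 10 weeks. These passages need reconciling.
3. State whether Aim 1 needs both hypotheses or either. If either, use a split alpha (0.025 each at one visit gives 1 − 0.975² = 4.9%) or a pre-stated order. A fixed sequence is only one option, and nothing in the documents ranks H1a above H1b.

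The cost is wording, with no added participants or scans, and slightly less flexibility. Splitting alpha costs power. If f = 0.45 (d = 0.9) applied to the imaging endpoints, which is an assumption, t-test power would fall from 79% to 69% at 20 per arm and from 75% to 64% at 18 per arm. On the same assumption, testing H1a first would block H1b in 21–25% of trials even when H1a is true. Requiring both hypotheses, or using one joint test for each, avoids ranking them.
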